2.0 Objectives*

2.1 The purpose of this study is to examine the efficacy of hookah tobacco public health education messages among young adults between the ages 18 to 30, including young adults who are susceptible non-users of hookah tobacco and current users.

2.2 Hypothesis 1: Messages will decrease hookah initiation among susceptible non-users and increase cessation among hookah users.

Hypothesis 2a: Message effects will be mediated by greater message engagement, message receptivity, and perceived harms of hookah tobacco.

Hypothesis 2b: Message effects will be greater among susceptible non-users versus hookah users and among those who do not use other tobacco products versus those who do.

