4.0 Study Endpoints*

4.1 The primary study endpoints among susceptible non-users are changes in susceptibility to use hookah tobacco, curiosity (i.e., intentions) to use hookah tobacco, and hookah tobacco initiation. The primary end

PROTOCOL TITLE: Randomized Trial Testing the Efficacy of Hookah Tobacco Public Education Messages among Young Adults

points among current hookah users are motivation to quit using hookah tobacco, frequency of hookah use, and cessation.

4.2 Secondary end points include perceived harm & addictiveness of hookah tobacco, perceived risk and worry about harm & addictiveness, and message-related outcomes including message receptivity, emotional response, and content recall. These will be examined as mediators of message effects. There are no safety outcomes in this trial.

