The primary outcomes and analytic approach will compare differences in 6-month outcomes across the control and messaging arms. We will initially assess differences in past 30-day hookah use behavior using longitudinal mixed effects logistic regression in the entire sample. The model will include past 30-day hookah use at 6 months as the dependent variable, trial arm, and baseline covariates for susceptible non-user/current user and any others identified in the steps outlined above.⁵⁵ We will then use a similar modeling strategy to assess differences by trial arm in hookah use initiation among participants who were susceptible non-users at baseline, and cessation among baseline users. These analyses will model dependent variables reflecting change in hookah use status from baseline to the 6-month follow-up separately for these two groups, a term for trial arm, and any covariates as identified above. Among susceptible non-users at baseline, we will similarly analyze changes in susceptibility status relative to trial arms as a secondary outcome. In both susceptible non-users and hookah users, will also conduct analyses to assess message effects on continuous outcome measures at 6 months, curiosity to use hookah tobacco and motivation to quit, respectively. We will use repeated measures ANCOVA to compare means of the continuous outcomes by trial arm at 6 months and Tukey's adjustment method for the pair-wise comparisons. In exploratory analyses, we will repeat these types of mixed logistic and ANCOVA analyses for outcomes measured at the 1- and 3-month time points. We will assess any potential message order effects separately in the education messaging arm by examining message effects by the 4x4 Balanced Latin Square orders. If any message order effects are detected or trends are observed we will include order as a covariate in analyses.⁵⁶ Exploratory analyses will also examine if responses to weekly assessments differ by message themes using approaches similar to those above.

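### Sections 4.1 and 17.1 give different primary endpoints beyond initiation and cessation, and no rule says how the primary results combine or how error is controlled across them

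*Combined protocol and SAP*

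**What the plan says.** **Hypothesis 1 (2.2):** "Messages will decrease hookah initiation among susceptible non-users and increase cessation among hookah users".

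**Endpoints (4.1, 4.2).** For non-users, "The primary study endpoints among susceptible non-users are changes in susceptibility to use hookah tobacco", followed by curiosity and initiation. For current users, the primary endpoints are "motivation to quit using hookah tobacco, frequency of hookah use, and cessation". The 4.2 list opens "Secondary end points include perceived harm" and continues with risk, worry and message-response measures. Susceptibility is not on it.

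**Analysis (17.1).** The analysis text opens "The primary outcomes and analytic approach will compare differences in 6-month outcomes across the control and messaging arms" without listing those outcomes. Its first model is introduced with "We will initially assess differences in past 30-day hookah use behavior" and covers the whole sample. Initiation and cessation follow, each in its own baseline group. Then comes "Among susceptible non-users at baseline, we will similarly analyze changes in susceptibility status relative to trial arms as a secondary outcome". The continuous analyses cover "continuous outcome measures at 6 months, curiosity to use hookah tobacco and motivation to quit, respectively", with no primary or secondary label.

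**Error control (17.1).** The power text uses a single two-tailed alpha of 0.05. The only multiplicity method named is Tukey's, for pair-wise comparisons of means.

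**The concern.** Initiation and cessation are not in doubt: Hypothesis 1, 4.1, the power text and the 17.1 analysis all include them. The doubt is about what else is primary and what counts as a positive trial. Two careful readers could draw up different primary lists and apply different success rules, and both could cite the protocol.

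The risk lies in reporting. If neither initiation nor cessation reached significance, a favourable result on curiosity, motivation to quit, susceptibility or pooled use could still be presented as a primary finding. A change in curiosity or motivation supports a different conclusion from a change in behaviour, and the background section says the trial is meant to inform FDA public education.

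**Working it through.** **1. The two sections side by side**

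| Outcome | 4.1 / 4.2 | 17.1 |
|---|---|---|
| Initiation (non-users) | primary | analysed, no secondary label |
| Cessation (users) | primary | analysed, no secondary label |
| Susceptibility (non-users) | primary | secondary |
| Curiosity (non-users) | primary | analysed, unlabelled |
| Motivation to quit (users) | primary | analysed, unlabelled |
| Frequency of use (users) | primary | no named analysis |
| Past 30-day use, whole sample | not listed | analysed first |

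Susceptibility is a direct contradiction and frequency of use an omission. Curiosity and motivation to quit are ambiguous. Pooled use is an addition, although it largely re-expresses initiation and cessation. Tukey's method does not help: with two arms there is one comparison of means per outcome at 6 months, and the method does not act across outcomes.

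**2. Chance of at least one false-positive primary result**

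Assumptions: no true effects; each endpoint tested once at two-sided 0.05 (inferred, since no per-endpoint level is written); any one success counts. The two baseline groups do not overlap, so their tests are independent. Within a group the tests are given a common correlation ρ, which the documents do not supply.

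For k independent tests the rate is 1 − 0.95^k:
- k = 2: 0.0975
- k = 4: 1 − 0.8145 = 0.185
- k = 6: 1 − 0.7351 = 0.265

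Simulated rates for correlated tests:

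| Primary set | ρ = 0 | 0.3 | 0.5 | 0.7 |
|---|---|---|---|---|
| Six in 4.1 | 0.265 | 0.254 | 0.235 | 0.206 |
| Four (initiation, cessation, curiosity, motivation) | 0.186 | 0.181 | 0.173 | 0.160 |
| Four plus pooled use | 0.202 | 0.197 | 0.188 | 0.174 |
| Initiation, cessation, pooled use | 0.115 | 0.115 | 0.115 | 0.115 |

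The pooled statistic is taken as (w₁z₁ + w₂z₂)/√(w₁² + w₂²), where z₁ and z₂ are the initiation and cessation statistics, w₁ = √(675 × 0.08 × 0.92) = 7.05 and w₂ = √(425 × 0.10 × 0.90) = 6.18.

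Counted within one baseline group, the rate is about 11–14% for three endpoints and 8–10% for two over the same range of ρ.

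**3. The protocol's power figures**

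Inputs from 17.1: 675 non-users, 8% vs 2.7%; 425 users, 10% vs 18%; two-sided 0.05; stated power 80% for each. The test is a pooled-variance comparison of two proportions with equal arms (337.5 and 212.5 per arm).

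| Two-sided level | Initiation, no dropout | Cessation, no dropout | Initiation, 70% retained | Cessation, 70% retained |
|---|---|---|---|---|
| 0.05 | 0.866 | 0.663 | 0.727 | 0.511 |
| 0.025 | 0.795 | 0.554 | 0.626 | 0.399 |
| 0.05/6 | 0.664 | 0.396 | 0.469 | 0.256 |

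The stated 80% is not reproduced for cessation, which needs 295 per arm. For initiation it is reached at 564 analysed, or 83.6% retention, a figure the plan does not state. This is a separate matter, but it means the costs below start from recalculated power. The 70% figure is an assumption, taken from the lower end of what 6.2 reports for earlier studies.

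**4. Cost of each success rule**

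Holm on two endpoints, both effects true: power = P(0.025) + [P(0.05) − P(0.025)] × P(0.025) of the other endpoint.
- Initiation, no dropout: 0.795 + 0.071 × 0.554 = 0.834
- Cessation, no dropout: 0.554 + 0.109 × 0.795 = 0.640 (from unrounded values)
- At 70% retention, the same formula gives 0.666 and 0.470

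Both must succeed at 0.05: 0.866 × 0.663 = 0.574 with no dropout; 0.727 × 0.511 = 0.372 at 70% retention.

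**The case against.** The strongest reply is that only susceptibility is flatly contradicted. Because 17.1 marks that one outcome secondary, curiosity and motivation to quit could be read as keeping their 4.1 status, and pooled use as a lead-in model for Hypothesis 1. That reading is reasonable, and it is why those items are called ambiguous here. It does not restore agreement on susceptibility, supply an analysis for frequency of use, or say whether the pooled result can support a primary claim.

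A second reply concerns size. 17.1 does not run six primary tests, and 4.1 is written separately for two groups that do not overlap, so error per group may be the relevant measure. This has force. With initiation and cessation as the only primaries and separate claims for each group, the error is 5% per group and no adjustment between them is needed. But the plan does not say this is the intended reading. With two or three primaries in a group, the per-group rate is still 8–14%.

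A third reply is that Hypothesis 1 joins the two outcomes with an and, so both must succeed. It is worded as a prediction, not a decision rule. If it is the rule, error is not inflated, but the joint power in step 4 applies and the sponsor should know it.

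**Conclusion.** The concern holds. The current text gives incompatible primary lists, most plainly on susceptibility and frequency of use, and states neither a success rule nor error control across endpoints.

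How much error this allows depends on which list is used. Under an any-one-counts rule it is 21–26% for the six in 4.1, 16–19% for the four that 17.1 analyses without a secondary label, 17–20% with pooled use added, 9.75% for initiation and cessation alone, and 11.5% for those two plus pooled use. All of these rest on an inferred 0.05 per test, no true effects, and assumed within-group correlations of 0.7 to 0. The contradiction between sections does not depend on any of those assumptions.

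This should be corrected. It is not graded higher because the two core outcomes can be identified throughout.

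**What to change.** 1. Make 4.1, 4.2 and 17.1 carry one identical primary list. The choice the documents best support is initiation in baseline susceptible non-users and cessation in baseline users. Susceptibility, curiosity, motivation to quit, frequency of use and pooled past 30-day use would then be secondary. The sponsor may keep others as primary, since the power text also covers continuous outcomes, provided they enter the error control.
2. State one success rule in advance:
   - **Either result may support an overall efficacy claim:** Holm at overall two-sided 0.05.
   - **Both must succeed:** each at 0.05.
   - **Separate group-specific claims:** each at 0.05, with no overall claim from one alone. This is defensible because the groups do not overlap and randomisation is balanced by use status.
3. Name an analysis for frequency of use.

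The change is wording only, with no extra participants or data. Power cost at the protocol's effect sizes:

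| Rule | No dropout | 70% retention (assumed) |
|---|---|---|
| Holm, two endpoints: initiation | 87% to 83% | 73% to 67% |
| Holm, two endpoints: cessation | 66% to 64% | 51% to 47% |
| Both must succeed (joint power) | 57% | 37% |
| Separate group-specific claims | no loss | no loss |
| All six kept primary, Holm's first step: initiation, cessation | at least 66%, 40% | at least 47%, 26% |

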6.0 Procedures Involved*

6.1 This study is a two arm prospective randomized trial to test the efficacy of public health messages about hookah tobacco use. All study procedures will be conducted by NORC staff in direct collaboration with the study team and investigators. Study participants will be anonymous to the study team and investigators, and all data collected as part of the study will be de-identified.

Participants will be recruited from the National Opinion Research Council's (NORC) AmeriSpeak consumer market research panel, screened for eligibility, and will complete a baseline assessment online. Then participants will be randomized in equal numbers to two arms: 1) hookah tobacco public education messaging or 2) control arm. On approximately a weekly basis for 4 weeks, participants will receive study communications and complete brief measures of message response online. For the hookah tobacco public education messaging arm, communications will consist of the study messages communicating about the health harms, addictiveness, social use, and flavorings in hookah tobacco. In response to each message, participants will complete measures of message response and hookah-related outcomes detailed below. Participants in the control condition will receive study communications with brief messages about health behaviors unrelated to tobacco (sun protection) and will complete the same measures. Study outcomes and hypothesized mediators will be assessed 2-, 4-, and 6-months after the message exposure period.

6.2 Trial participants will be 1,100 English speaking young adults ages 18 to 30 years old who have never used hookah tobacco but are deemed susceptible based on four screening questions or report hookah tobacco use at least once within the past month on valid measures. Trial participants will be recruited from the AmeriSpeak national consumer research panel maintained and operated by NORC. Although recruitment and data collection procedures will be conducted by NORC and all study participants will be anonymous to the investigators, our team will work collaboratively with NORC AmeriSpeak staff to oversee recruitment,

PROTOCOL TITLE: Randomized Trial Testing the Efficacy of Hookah Tobacco Public Education Messages among Young Adults

enrollment, data collection, and experimental procedures.

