The online baseline assessment includes valid measures of hookah and other tobacco use behavior, hookah beliefs, perceptions, and other constructs from our conceptual framework. After completing a baseline, participants will be randomly assigned in approximately equal numbers to one of two arms: 1) hookah tobacco education messaging; 2) control arm. Randomization will be balanced by hookah use status (susceptible non-user, current user) to ensure sufficient numbers of these characteristics across study arms. Participants in the hookah education messaging arm will then receive 4 study communications delivered approximately weekly during the exposure period. These communications will consist of: 1) the study hookah education messages; and 2) brief post-message (approximately 5 minutes) measures of hookah use behaviors, beliefs and perceptions, and message responses. Procedures for participants randomized to the control arm will be similar, however communications will consist of non-tobacco messages communicating about sun protection that we have developed on our previous work and pilot tested against tobacco-related messaging to ensure they are an adequate contact-matched control. Messages will have a similar layout and structure (e.g., amount of text) to the hookah public education messages and will be presented in a consistent order for all participants. We chose this contact-matched control arm to ensure groups are treated equivalently with only message content varying between arms.

PROTOCOL TITLE: Randomized Trial Testing the Efficacy of Hookah Tobacco Public Education Messages among Young Adults

All participants will complete follow-up assessments online 2-, 4-, and 6-months after the message exposure period. We chose these time points based on our team's prior work on young adult tobacco use behavior and messaging,^{44, 45} other research on hookah tobacco messaging,²¹ recommendations for follow-up in tobacco intervention research,^{47, 48} and because this follow-up frequency and duration will capture short term message effects and changes in hookah use, susceptibility, and mediating processes.^{12, 14, 21, 47, 49-52} As with the baseline, follow-ups will be securely administered online. Measures are attached in Section 14. At the conclusion of the final follow-up, all participants will be debriefed on the study goals and the potential risk of hookah and other forms of tobacco use.

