10.0 Inclusion and Exclusion Criteria*

10.1 NORC AmeriSpeak panel members will be recruited and screened for eligibility through a series of steps. NORC will send an email invitation using their standard template to potential participants and will introduce study procedures and eligibility criteria to AmeriSpeak panel members. Interested panel members will be directed to the online eligibility screener with valid self-report items to confirm eligibility. Invitations will be targeted by NORC using data from the member panel enrollment profile (i.e., participant age) and confirmed based on responses to the brief online eligibility screener.

10.2 Eligible participants for the randomized trial will be 1) young adults ages 18 to 30; 2) who have never used hookah tobacco but are deemed susceptible based on 4 screening questions or report hookah tobacco use at least once within the past month based on valid measures;²³ ²⁴ and 3) are NORC AmeriSpeak panel members residing in the US.

Study exclusion criteria include: 1) individuals who are younger than 18 or over 30 years of age; 2) those who do not meet self-report criteria for susceptibility or current use of hookah tobacco; or 3) are not registered to participate in research studies through the NORC AmeriSpeak panel.

10.3 Study participants will be Amerispeak panel members who meet the eligibility criteria listed above. The following special populations will be excluded: Adults who are unable to consent, individuals who are not yet adults, pregnant women, and prisoners.

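### Susceptibility among non-users is analysed only as a yes/no status, although all of them enter as susceptible; a baseline-adjusted four-item score should be added

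*Combined protocol and SAP*

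**What the plan says.** Section 4.1 gives the primary endpoints for susceptible non-users as "changes in susceptibility to use hookah tobacco, curiosity (i.e., intentions) to use hookah tobacco, and hookah tobacco initiation". It does not say that susceptibility is to be reduced to a yes/no form.

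Section 17.1 does so. After describing logistic models for change in use status (initiation, cessation), it adds that among baseline non-users "we will similarly analyze changes in susceptibility status relative to trial arms as a secondary outcome". This is the only susceptibility analysis in the plan, and it ranks the endpoint as secondary where section 4.1 ranks it as primary. The ANCOVA is reserved for "message effects on continuous outcome measures at 6 months, curiosity to use hookah tobacco and motivation to quit, respectively", so susceptibility is not among the continuous outcomes.

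Under section 10.2, non-users qualify only if they "have never used hookah tobacco but are deemed susceptible based on 4 screening questions". Section 6.2 gives the same rule.

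The response options, scoring, cut-off and follow-up content of the four questions are not in the text. Section 6.2 says only "Measures are attached in Section 14", and that attachment is not part of the material.

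**The concern.** Because eligibility requires susceptibility, baseline status is a constant among non-users. It cannot act as a covariate, and the only change it can register is a move to not susceptible. A participant who becomes much less inclined to try hookah but stays above the cut is recorded as unchanged. So is one who becomes more inclined. If the four items are graded, a score would register both kinds of movement and would have a baseline value that varies between people.

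What is at stake is the sensitivity of one endpoint. Section 17.1 expects only 8% of non-users to initiate over six months, so the behavioural endpoint rests on few events. A sensitive measure of susceptibility is worth more in that setting.

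**Working it through.** Section 17.1 gives no power, effect size or expected rate for susceptibility, so there is no plan figure to reproduce. The calculations below show what the choice of status over score could cost.

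**Inputs from the protocol.** 675 non-users, 1:1 allocation, two-sided alpha 0.05 (sections 6.2, 12.1, 17.1). Retention of 70% or more in similar studies (section 6.2), which leaves 0.70 × 675 ≈ 472, or 236 per arm. Earlier effect of d = 0.34 on intention in susceptible non-users, and 49% of never-users susceptible in that study (section 3.2).

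**Assumptions not in the protocol.** Share no longer susceptible at 6 months, p = 10% to 50%; a roughly normal score; baseline to 6-month correlation r = 0.5; and, for one illustration, a shift of d = 0.20.

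**Step 1. Information kept by the split.** Relative to a normal score, the efficiency of a yes/no split is e = φ(z_p)² / [p(1 − p)].

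- p = 10%: 0.1755² / 0.09 = 0.342, a loss of 66%.
- p = 25%: 0.3178² / 0.1875 = 0.539, a loss of 46%.
- p = 50%: 0.3989² / 0.25 = 0.637, a loss of 36%.

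**Step 2. Power at d = 0.20 with all 675.** Power ≈ Φ(d√N/2 × √e − 1.96), and d√N/2 = 0.20 × 25.98 / 2 = 2.598.

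| Analysis | Calculation | Power |
|---|---|---|
| Status, p = 10% | Φ(2.598 × 0.585 − 1.96) | 33% |
| Status, p = 25% | Φ(2.598 × 0.734 − 1.96) | 48% |
| Status, p = 50% | Φ(2.598 × 0.798 − 1.96) | 54% |
| Score, unadjusted | Φ(2.598 − 1.96) | 74% |
| Score, adjusted for baseline, r = 0.5 | Φ(2.598 / √0.75 − 1.96) | 85% |

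A direct two-proportion calculation for status gives 36%, 50% and 54%, in line with the table. With 472 people the same formulas give 25% to 41% for status, 58% for the score and 71% for the adjusted score.

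**Step 3. Like-for-like comparison.** The graded baseline score could also enter the logistic model for status. Simulating that model in the same setting gives status about 40% power at p = 10%, rising to about 60% at p = 50%. The adjusted score still has 85%.

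**Step 4. Larger effects, 236 per arm, neither analysis adjusted.** Status is shown for 50% / 80% / 90% of controls still susceptible.

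- d = 0.34: score 96%; status 83% / 77% / 64%.
- d = 0.25: score 77%; status 58% / 50% / 39%.

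**Step 5. Departure from normality.** Four four-category items were simulated, with status defined as any item above the lowest category and all entrants susceptible. Inter-item correlation ran from 0.5 to 0.85 and the baseline to follow-up correlation of the underlying trait from 0.4 to 0.85. Over all settings the loss ran from 6% to 69%. Where 46% to 60% of never-users were susceptible, near the 49% in section 3.2, the loss from using status was:

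- 19% to 37% with neither analysis adjusted;
- 21% to 52% with both adjusted;
- 23% to 58% for unadjusted status against the adjusted score.

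**The case against.** A reader might infer that the trial is bound to throw away a third to two thirds of its information on susceptibility. The documents do not support that. The range needs a near-normal score and 50% to 90% still susceptible, and neither is stated. With few response options and many people at the floor, the loss can be small.

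A reader might also set 33% to 54% directly against 85%. That is not like for like: section 17.1 allows covariates in these models, so the baseline score could adjust the status analysis too. The gap then narrows, although it does not close. The correlation of 0.5 may also be generous, because admitting only susceptible people restricts the baseline range. If 0.5 held among all never-users and half were susceptible, it would be about 0.33 among entrants. The adjusted score would then have Φ(2.598 / √(1 − 0.33²) − 1.96) ≈ 79% power rather than 85%.

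The shift of 0.20 SD has no source in the protocol. At the sponsor's earlier effect of 0.34, status has 64% to 83% power even with 70% retention. A smaller effect six months after exposure is plausible, but the size of the gap depends on the effect chosen.

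It is fair to add that curiosity, which section 4.1 equates with intentions, is already a continuous outcome in the same people. A real message effect would therefore not necessarily go unseen. Leaving the susceptible category is also a clear question tied to the entry definition, and deserves reporting.

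These points limit the size of the claim. They do not remove the gap: no graded susceptibility analysis is planned, no baseline susceptibility score is named as a covariate, and the follow-up outcome is dichotomised in any case.

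**Conclusion.** The point holds in a conditional form. It follows from the eligibility rule and section 17.1 alone that baseline status carries no information among the 675 non-users, and that movement which does not cross the cut is not counted.

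The size is uncertain. The loss is about 36% to 66% for a near-normal score with 50% to 90% still susceptible, and may be much less for a discrete score with a floor (6% to 69% across the simulations). In the d = 0.20 illustration, the fair comparison is about 40% to 60% power for adjusted status against 85% for the adjusted score, or about 79% if range restriction lowers the correlation to 0.33.

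The reading to avoid is that the trial as a whole is underpowered or will miss a message effect. The gain is confined to the susceptibility endpoint, and it depends on the four items being graded and asked again at follow-up. Repetition is a reasonable inference, since change in status is an outcome, but the text does not state it. This is a cheap improvement to the analysis, not a flaw that undermines the trial.

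**What to change.** In section 17.1:

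- Pre-specify an analysis of the four-item susceptibility score at 6 months with the baseline score as covariate, provided the items are repeated at follow-up. Use ANCOVA, or proportional odds if the score is skewed or crowded at the floor.
- Define the score, the response options and the cut for status.
- Keep the share no longer susceptible as a reported result.
- Keep participants who initiate in the analysis under a stated scoring rule, for example the highest category. Dropping them would be an exclusion after randomisation based on an outcome.
- Reconcile sections 4.1 and 17.1 on whether susceptibility is primary or secondary.

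The choice should be fixed before outcome data are seen by arm, so that score and status are not chosen between afterwards. The cost is SAP wording, one extra analysis and a mean score that is less familiar than a yes/no result. No extra participants are needed and, if the items are already repeated, no extra questions.
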